# Recruitment Strategy Recruitment of Mentees

Mentees (n=300; 150 mentored, 150 support group) will be primarily recruited by a direct mailing to female African American lupus patients currently enrolled in the MUSC P30 Core Center for Clinical Research (CCCR) SLE database who have agreed to future contact as well as lupus patients from the MUSC clinics not in the registry. Flyers containing the same information contained in recruitment letters will be posted in MUSC lupus clinics and shared with local SLE support groups, other SC rheumatologists and arthritis health professionals, and local chapters of the Lupus and Arthritis Foundations for distribution to their patrons. If target recruitment is not achieved within the desired timeframe by self-selection, patients will be approached individually during clinic encounters, by phone, and/or repeated mailed/emailed or patient health record portal invitation. Patients who have indicated that they are willing to be contacted for future research in their MCRC consent forms will serve as the base for these invitations. Recruitment letters and flyers will also be shared with other academic medical institutions with eligible patient populations. Patients outside of the MUSC system who express interest will still be able to participate. They will not be required to travel to MUSC as informed consent can be obtained and questionnaires completed via REDCap, study materials can be mailed, and all other study activities can be achieved by phone.

#### Recruitment of Mentors

Potential peer mentors will first be invited from PALS pilot participants (mentees and mentors) (n=30), with the intention of retaining mentors to mentor multiple groups of mentees over the course of the study. It is expected that everyone would benefit from the use of experienced mentors, and using experienced mentors over time is also consistent with future real-world implementation. As needed (up to n=60, but approximately n=30 expected to be needed based on past research participation and interest), potential peer mentors who are considered competent in the management of their conditions will be identified by MUSC rheumatologists and subsequently trained by the PI. As part of the ongoing MUSC SLE database, patients are regularly flagged who providers deem competent enough to speak with the media on behalf of the patient population. We will mail out recruitment letters that will explain the study and provide participants a number to call if they are interested in participating. Participants who indicate interest in the study will be contacted by telephone to conduct a pre-screening assessment. If eligibility criteria are met, the screening/enrollment visit will be scheduled. As part of the mentor screening interview with the PI, psychosocial status will be assessed using the psychological scales of the Arthritis Impact Measurement Scales (AIMS), the Arthritis Helplessness Index (AHI), Wallston General Perceived Competence Scale, University of California at Los Angeles (UCLA) Loneliness Scale, Rosenberg Self-Esteem, Campbell Personal Competence Index. Carkhuff Communication and Discrimination Skills Inventories, and the Applied Knowledge Assessment (AKA) scale.[113] The PI will make a determination of competence, maturity, emotional stability, and verbal communication skills after overall assessment during the screening interview and training. Additional recruitment strategies will include the identification of local SLE support group members who have emerged as natural helpers, referrals from other rheumatologists and arthritis health professionals, and outreach to the local chapters of the Lupus and Arthritis Foundations by letter and telephone. Others have used these approaches successfully in multiple studies.

# Study Eligibility criteria

Inclusion criteria for mentees and mentors include: 1) African American race/ethnicity and female gender; 2) clinical diagnosis of SLE from a physician, according to ACR revised criteria for SLE.[110]; and 3) 18 years of age or older. Additional inclusion criteria for mentors include: 1) disease duration > 2 years; 2) able to attend scheduled training sessions; and 3) willing to provide one-on-one support to up to three African American women with SLE. Mentees who participated in the pilot will be ineligible to participate in this study as a mentee, but could participate as a mentor if they meet other eligibility criteria.

# B4g. Overview of the Peer Mentoring Intervention

Peer Mentoring Intervention Elements

Mentor Training: The principal roles of the peer mentors are to: 1) provide information about SLE, SLE-related behaviors, thoughts, and feelings, and the nature of recommended treatments; 2) provide social

support to alleviate the mentee's sense of social isolation; 3) enhance and reinforce the mentee's sense of self-efficacy to manage their condition; and 4) encourage the mentee to participate actively in the recommended self-management skills building therapy. Mentors will be trained in conversational strategies to help them meet the objectives without being overly directive and will be instructed not to give clinical advice.[114] Upon enrollment, peer mentors will receive 12 hours of training, broken into two 6-hour blocks, prior to working with mentees.[114] Mentors will be given a written manual presenting all the material in detail for their ongoing reference. The training manual was developed in collaboration with social work leadership from Hospital for Special Surgery's LupusLine® Program. The program, led by the Department of Social Work Programs, is a free telephone counseling service staffed by trained volunteers who have SLE or are close family or friends of people living with lupus.[113,115] Training will will include the following:

- 1) Review of slide presentation and rationale for learning self-management, as well as the contribution of biological, psychological, and social factors to the SLE experience;
- 2) demonstration and practice of some basic skills to use in working with the mentee;
- 3) review of the manual; outline of the format and required elements for each call;
- 4) participation in role-playing exercises in pairs to learn ways of presenting didactic information, supporting positive statements, and responding to questions posed by the mentee:
- 5) participation in question development and topic starter exercises;
- 6) participation in troubleshooting exercises to suggest ways of addressing particular problems; and
- 7) review of call formats, reporting requirements and detailed discussion of emergency situation procedures.

Mentee pairing: After enrollment and completion of baseline assessments, mentees will be matched with peer mentors based on as many specific shared concerns of their experiences as possible. Potential matching areas include disease symptoms, parenting, work-related concerns, similarity of life stage (including age)]41] and demographics (including area of residence), similarity of personality characteristics, and peer mentor availability, and will be assessed as part of the screening process.

### Overview and Description of the PALS Intervention:

Recruitment and enrollment: This will occur in 3 waves. Within each wave, each mentor will be assigned all of their mentees at one time to ensure that intervention activities occur within the same 12-month period. As mentor:mentee quads (1 mentor, 3 mentees) are identified, they will attend an introductory session together, during which the mentoring process will be discussed, including time commitment, roles, responsibilities, benefits, and ground rules, and mentees and peer mentors will have the opportunity to ask questions and make informed decisions about their ability to fully participate in the intervention. If face-to-face meetings are not possible for all members of the quad, skype or another form of video meeting will be attempted. Mentees will be informed that she will be dropped from the study if she misses three consecutive or four of the 12 total educational sessions for non-emergency reasons; peer mentors will only be permitted to miss three educational sessions in total. Any missed educational content on the part of the mentee or mentor will be added to subsequent sessions and emphasized in booster sessions.

Description of The PALS Program: The program will consist of 12 sessions of peer mentoring that will include one standard educational session by telephone or video for approximately 60 minutes every 2 weeks. Additional interaction will be discouraged, but mentees and mentors will be asked to report any additional social interaction should it occur. The bi-weekly educational session will be generally structured in three parts: introduction, structured education, and problem solving. 60-minute calls are necessary for the delivery of educational content and mentors and mentees to be able to discuss their own experiences and potential solutions. Bi-eekly content has been adapted from the six modules of the Chronic Disease Self-Management Program (CDMP), Arthritis Self-Management Program (ASMP), and Systemic Lupus Erythematosus Self-Help (SLESH) Course,[61,116] and further tailored to African American women with six added sessions based on cultural issues reported as important to African Americans in earlier research conducted by the PI[93,117] and documented unmet needs in the African American SLE patient community.[94,95]

Tailoring of the PALS intervention: To address unmet needs around understanding the medical regimen, including considerations around depression, medication concerns, and physical symptoms, culturally relevant sessions on 'Complications' and 'Self-monitoring' were developed. In response to unmet needs

around trust in the provider, communication with providers, and receiving adequate information from medical staff about treatment side effects, sessions on 'Coping' and 'Trust' were developed, Lastly, unmet needs around having access to telephone support and advisory services and having assistance with knowing which symptoms should trigger a doctor visit[35,37,77] are addressed by the PALS study design (i.e., telephone/video delivery of intervention) and sessions devoted to less frequently discussed topics of 'Body image' and 'Sexuality/sexual health'. The PALS pilot was then used for initial refinement of the intervention protocol. We analyzed qualitative responses that were collected as part of weekly mentee check-ins, mentor logs, and the end-of study focus group. Themes that emerged included: a) interpersonal, familial and romantic relationships; b) individual experiences of living with SLE; and c) physician-patient relationships. Additional themes emphasized how the intervention worked bidirectionally wherein both mentors and mentees were empowered toward greater disease self-efficacy. We found that: 1) empowerment was facilitated/achieved by mentors taking their mentorship responsibilities seriously and seeking several avenues for collaboratively developing success with their mentees: 2) mentors felt empowered through being able to discuss topics that they felt were often marginalized by healthcare professionals, such as sexuality; and 3) the intervention encouraged reciprocity. Such dynamic discussions served as a participative approach to determining which components of the intervention were most useful to participants. Based on observed themes, unique concerns of our study population have been built into the proposed intervention. Specifically, the importance of faith and spirituality in coping with their disease, the impact of chronic pain on their interpersonal, familial, and romantic relationships, the need for more sensitivity in interactions with medical staff, and the importance of support and relationship building in mentee-mentor interactions have been incorporated into session 4: effective communication, session 10: self-monitoring, and session 11: sexuality, of the PALS implementation plan and training protocols, to ensure that culture-bound myths and concerns about SLE are addressed in this cultural group.[97]

Control Intervention (Support Group): Mentees randomized to the social support control group will be enrolled in a lupus support group designed specifically for this project. Unlike traditional support group meeting formats that are open to all lupus patients, family members, friends and supporters; advertised publicly; implemented by a trained facilitator; and generally include a specific discussion topic or an informative presentation, the PALS-specific support group will be limited to PALS control participants, be moderated by a PALS study coordinator who will not provide any information or discussion topics, and will simply provide a meeting session via WebEx for social support control participants to interact on a biweekly basis.

Treatment Fidelity: At the onset of the study, peer mentors will receive extensive training. [name] will provide training in pathophysiology, clinical management, and effective strategies of lifestyle management in SLE. [name] will provide primary training on peer-mentoring and monitor counseling skills using audit and feedback. [name] will provide training on social support, telephone engagement and follow up and conflict resolution.[111,112] In addition, [name] will provide ongoing oversight of peer mentoring sessions. Training will consist of two full days of information and role-playing and then one day booster sessions in years 2-5 to minimize drift in peer mentoring skills.[102] After initial training, peer mentors will continue to meet with the PI bi-weekly to identify challenges and reinforce the guidelines for peer mentors.[114] Mentors will be required to submit logs of the number of calls made, number of hours spent with mentees, and content covered during that two-week period, in order to be compensated. To assess the frequency and duration of calls, other interactions with their mentor and whether specific content has been covered, mentees will receive a link to a brief REDCap survey by email and/or text message every two weeks. Additionally, a subset of sessions will be recorded to allow direct evaluation of the contents of interactions. Self-report assessments will be used to track the effectiveness of the intervention. Fidelity will be considered acceptable if: 1) a given participant completes at least 9 of 12 sessions (peer mentoring or support group) or receives corresponding content and achieves at least 9 hours of interaction; and 2) all assessments (baseline, mid-intervention, and post-intervention) are completed within 1 week of distribution.

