created for this project, on the same schedule as peer mentoring sessions. Both conditions will be delivered via Webex, which has several advantages for this intervention: 1) Sessions are easily accessible via phone or computer, allowing participants to choose their preferred interaction style; 2) A study coordinator can host the support groups and drop in/out for monitoring purposes; 3) There are video- or voice-call options for up to 25 participants at a time; and 4) This application ensures concordant delivery methods across both arms of the study and the ability to document the frequency that voice and video options are used to adjust for participant choices in analyses. All participants (mentees, mentors, and social support controls) will be assessed using validated measures of patient reported outcomes and clinical indicators of disease activity at baseline, mid-intervention (3 months from baseline), immediately post-intervention (6 months from baseline), and 6 months post-intervention (12 months from baseline). For each wave, outcomes for mentees randomized to the mentored group will be compared with the outcomes of mentees randomized to the support group. A booster session will be incorporated for all participants (mentored and support group) at 3 months post-intervention to encourage retention.[102]

B4c. Scientific Rigor: Assuming 3 post-randomization measurement time points, level of significance p=0.05, two-tailed comparison, correlation between pairs of measurements within participants (interclass correlation) no larger than p=0.7, AR(1) covariance structure, we estimate that 123 participants per group (total n=246) are needed to detect, with 80% power, a standardized effect size of 0.35sd with 20% inflation for attrition at 12 months. This study will apply strict principles of randomized clinical trials including randomization, blinding, careful tracking of all participants and intent-to-treat analyses to ensure robust and unbiased results.

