Randomization Procedure: Participants recruited for the mentored or control (support group) portion of the study will be randomized using a block randomization procedure to assure equal sample sizes in the mentored and control groups. Using a block size of 3, participants will be assigned to the appropriate treatment condition as they enroll in the study until the block is completed. Then the following 3 participants will be assigned based on the next block.[144] Once a patient is randomized and attends the first session, she will be entered into the study and included in the intent-to-treat analysis plan. Subjects will remain blinded to group allocation until after the completion of baseline assessment. The only members of the research team who will be aware of randomization assignment will be the Research Coordinator, and the statistical analyst in charge of randomization. Randomization will occur at the patient level. As such, we will take the following steps to minimize contamination between the two arms of the study: 1) patients in the intervention and control arms will be instructed not to share intervention materials with family members, friends, or other clinic patients; 2) patients will be given instructions not to disclose their treatment assignment to their assessment interviewers.

Data Management: Data will be captured via REDCap (a free, secure, web-based application) and overseen by a data management and analysis team comprising statisticians at MUSC. Data will be collected electronically in password-encrypted files. A part-time masters-level statistician will be responsible for data management. Data will be reviewed on a bimonthly basis and issues will be communicated to the project coordinators. In particular, outlying and inconsistent data values, as well as missing data, will be the targets of the data quality review.

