AIM 1: Determine the efficacy of a peer mentorship intervention in African American women with SLE on disease self-management and HRQOL. Analyses for Aim 1 will focus on estimation of efficacy as determined by: (a) change in quality of life; and (b) change in self-management. Estimates of effect sizes for outcome variables will be reported as point estimates (mean differences between pre-post measures. as appropriate) and interval estimates (95% CI) with two-sided p-vales denoting statistical significance to provide an indication of the presence of a clinically important treatment effect. [145,146] A p-value of 0.05 will be considered to be statistically significant. After studying the distributions of baseline characteristics. we will use a generalized linear mixed model regression model to determine if the intervention will produce a greater change in the main outcomes from baseline. This model will include time, treatment (along with their interaction), and covariates (including the amount of intervention received, demographic factors, medications, coping, depression, stress, anxiety, health literacy, trust, and social support) as fixed-effects. Using the amount of intervention, which is measured as an aggregate number of sessions completed or hours of interaction as a covariate would allow us to study the dose response. In the generalized linear mixed model (GLMM), we will use different link functions depending on the assumed distribution of the response variable. For binary outcomes, we will use logit link and for count outcomes we will use log link under a poisson or negative binomial distribution. For example, for the a given quality of life variable, HRQOL measured at baseline, month 3 and month 6, we will include intervention group, time, and time X intervention as the primary independent variables in the basic (unadjusted) model, and covariates that are not balanced at randomization (or a propensity score based on these covariates) will be added in the subsequent (adjusted) model to adjust for the possible confounding effect of these variables. Unadjusted and covariate-adjusted least squares means for each outcome variable will be compared at the primary time point (month 12) and at intermediate secondary time point (month 6) using appropriate model contrasts and the Tukey-Kramer adjustment for multiple comparisons for the secondary time points. These contrast comparisons, along with corresponding 95% CI, will provide estimates of the difference in outcome means (effect sizes) for the hypothesized comparisons.

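### The attendance rule drops mentees from the study, and no text keeps them in follow-up to month 12, which conflicts with the intent-to-treat commitment

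*Combined protocol and SAP*

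**What the plan says.** **The rule.** Under Overview and Description of the PALS Intervention (Recruitment and enrollment), each mentee is to be told that "she will be dropped from the study if she misses three consecutive or four of the 12 total educational sessions". The full condition is "four of the 12 total educational sessions for non-emergency reasons". The same paragraph adds that "Any missed educational content on the part of the mentee or mentor will be added to subsequent sessions", without saying that this cancels an absence. What counts as an emergency is not defined.

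**The commitments.** B4c (Scientific Rigor) promises "careful tracking of all participants and intent-to-treat analyses to ensure robust and unbiased results". Randomization Procedure says: "Once a patient is randomized and attends the first session, she will be entered into the study and included in the intent-to-treat analysis plan".

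**The end point.** The AIM 1 analysis text makes month 12 the primary time point. The sessions end at 24 weeks (B4b, Study Overview).

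**Other uses of attendance.** Treatment Fidelity calls delivery acceptable if "a given participant completes at least 9 of 12 sessions (peer mentoring or support group) or receives corresponding content", together with at least 9 hours of interaction and timely assessments. The AIM 1 analysis text enters dose in the model, "Using the amount of intervention, which is measured as an aggregate number of sessions completed or hours of interaction as a covariate", in order to study dose response.

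**The control arm.** The support group is "moderated by a PALS study coordinator who will not provide any information or discussion topics". No attendance rule is stated for it.

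**Missing data.** The AIM 2 and Missing data paragraphs plan mixed models under missing at random, maximum likelihood and multiple imputation.

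**The concern.** A rule that ends study participation because of poor attendance makes the presence of an outcome depend on adherence after randomisation. Women who miss sessions short of an emergency may do so through low engagement, fatigue or low mood, and these may also go with poorer quality of life, activation and disease activity at month 12. If the rule operates in the mentored arm only, the observed month-12 comparison sets mainly adequate attenders against support-group women of every attendance level. That favours mentoring even if mentoring does nothing. It also thins out the low end of the attendance range that the dose-response analysis needs. Outcomes that were never collected cannot be restored at the analysis stage.

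**Working it through.** **1. Does a drop end assessments?** The rule says the study. No section provides for assessing a dropped mentee. For mentors, the Data Collection Schedule under Collection of Data and Specimens does say that assessment continues whether or not a mentor has mentees, so continued follow-up was written down where it was intended. Loss of later assessments is therefore the natural reading, but it is an inference.

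**2. Which arm?** The rule sits in the text on mentor-mentee groups and concerns educational sessions, which the support group lacks. Treatment Fidelity names both conditions when it means both; this rule does not. On the other side, Recruitment of Mentees and Control Intervention use the word mentees for both arms. One-sided application is probable, not stated.

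**3. The plan's sample size.** Inputs from Power and Sample Size Justification: two-sided 0.05, 80% power, 0.35 SD, correlation 0.6 with compound symmetry, 20% inflation.

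n per group = 2 × (1.96 + 0.84)² × 2(1 − 0.6) / 0.35² = 102.5, and 102.5 × 1.2 = 123.0. This matches the stated 123. Recruitment is 150 per arm.

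**4. Share dropped.** Assume independent absences with probability p per session. Four or more absences trigger the rule. With exactly three absences it triggers only if they are consecutive, which can happen in 10 ways:

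P(drop) = P(Bin(12, p) ≥ 4) + 10 p³(1 − p)⁹

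| Attendance | P(drop) | Of 150 |
|---|---|---|
| 90% | 0.026 + 0.004 = 0.030 | 4 |
| 85% | 0.092 + 0.008 = 0.100 | 15 |
| 80% | 0.205 + 0.011 = 0.216 | 32 |
| 75% | 0.351 + 0.012 = 0.363 | 54 |

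Among women who attended the first session, as entry to the intent-to-treat set requires, only 11 sessions can be missed. The formula becomes P(Bin(11, p) ≥ 4) + 9 p³(1 − p)⁸, which gives about 2%, 8%, 17% and 30%.

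**5. Bias with no true effect.** Let dropping have correlation r with the month-12 change, and let a share d of the mentored arm be dropped. The SD of change is √(2 × 0.4) = 0.894. The observed-data bias is r × 0.894 × φ(z_d)/(1 − d), where φ is the normal density and z_d the d quantile.

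- At d = 0.20: φ/(1 − d) = 0.280/0.80 = 0.350, so the bias is 0.313r. That is 0.09 SD at r = 0.3 and 0.16 SD at r = 0.5.
- A simulation with the same covariance, keeping baseline and month 3 and fitting month 12 by missing-at-random likelihood, leaves 0.07 and 0.11 SD. That is about a fifth to just under a third of 0.35.
- At d = 0.10 the likelihood bias is 0.04 to 0.06 SD. At d = 0.03 it is about 0.01 to 0.02 SD.
- If dropping depends only on baseline and month-3 values, or if month 12 is still collected, the likelihood bias is about 0.

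The simulation is favourable in one respect. A woman who misses sessions 2 to 4 is dropped by about week 8, so she may have no month-3 value either.

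**6. Power.** With 20% loss in controls and 30% or 40% in the mentored arm, power is 75.5% or 71.9% at 123 per arm, but 83.4% or 80.1% at 150 per arm.

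**The case against.** The sponsor has a fair reply on several counts.

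- Nothing says that assessments stop. The rule describes what mentees are told, and Randomization Procedure keeps every woman who attends the first session in the analysis set. This stands as an ambiguity. It does not resolve the conflict, because being in the analysis set does not provide a month-12 measurement.
- A reader might infer that the mentored arm becomes completers only. The documents do not support that: dropped women's baseline and earlier data enter the mixed model or the imputation. What is at risk is the observed month-12 data, with the rest resting on missing at random. The planned check on predictors of missingness cannot test dependence on unobserved outcomes.
- A reader might infer that the sickest women are removed. The non-emergency condition should spare some illness-related absences, so this is not established. With emergency undefined, fatigue or a non-acute flare could still count.
- A reader might equate the rule with the 9-of-12 fidelity criterion. They differ: three consecutive absences can leave 9 sessions completed, fidelity also accepts corresponding content, and emergency absences do not count towards the rule. The dose range is narrowed, not eliminated.
- Recruiting 150 against 123 required cushions power, so the rule does not by itself exhaust the attrition allowance.
- Every attendance rate and correlation used here is assumed. The only related figure is 10% attrition in the pilot.

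**Conclusion.** The point holds in a limited form. As worded, the rule ends study participation for poor attendance, probably in the mentored arm only, and no text preserves the primary time point for those women. It therefore conflicts with the intent-to-treat and tracking commitments and weakens the dose-response analysis. If it is applied that way, the month-12 data come mainly from adequate attenders, and the planned methods remove the bias only if dropping depends on observed data alone.

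The size is uncertain. It runs from negligible (about 3% dropped at 90% attendance) to a false benefit of roughly 0.07 to 0.11 SD at 20% dropped, given an assumed correlation of 0.3 to 0.5 and independent absences. If the rule were meant for both arms, the asymmetry would shrink but the conflict with intent-to-treat would remain. It would go too far to say that outcome loss is certain or that the comparison is beyond rescue. Because a sentence can settle the ambiguity and uncollected outcomes cannot be recovered, it should be settled before follow-up is lost.

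**What to change.** Reconcile the attendance rule with B4c and Randomization Procedure:

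1. State that missed sessions do not end study participation. Whatever the sponsor decides about further sessions, a woman who reaches the limit is still assessed at months 3, 6 and 12 and analysed in her randomised arm, unless she withdraws consent. Align the participant wording.
2. Say which arm or arms the rule covers, define emergency, and record attendance by the same definition in both arms.
3. Use the 9-of-12 criterion only to describe fidelity or to define a sensitivity set.
4. Add a missing-not-at-random sensitivity analysis for month 12, for example a shift applied to the imputed values of dropped women over a stated range.

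The cost is a short protocol change and some extra follow-up effort. Recruitment of Mentees already provides for remote questionnaires through REDCap, but SLEDAI may need a clinic visit with bloods when no recent score is in the database. The estimated effect may be smaller once low attenders are counted.
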